Title:

**Fast-track Surgery After Gynecological
Oncology Surgery**

NCT number: NCT02687412

Date of the document: January 18, 2017

Fast-track surgery after gynecological oncology surgery: study protocol for a randomized controlled trial

[name] , [name], [name]. Department of Gynecological Oncology, Second People's Hospital of Sichuan, Sichuan Cancer Hospital, Chengdu 610041, Sichuan, People's Republic of China.

[name] e-mail:[contact]

[name] e-mail: [contact]

[name] e-mail: [contact]

Abstract

Background

Fast-track surgery (FTS) pathway, also known as enhanced recovery after surgery (ERAS), FTS is a multidisciplinary approach aiming to accelerate recovery, reduce complications, minimise hospital stay without an increased readmission rate and reduce healthcare costs, all without compromising patient safety. The FTS pathway have been adopted by most surgical specialties worldwide, and it has been used successfully in non-malignant gynecological surgery, but it has been proven to be especially effective in elective colorectal surgery.

The advantages of fast-track principles that have been documented in connection with abdominal surgery most likely extend to the field of gynecology, but this is only an assumption, since fast-track in elective gynecological surgery has not been studied carefully so far. However, no consensus guideline has been developed for gynecological oncology surgery although surgeons have attempted to introduce slightly modified FTS programmes for patients undergoing such surgery. NO randomised controlled trials for now.

The advantages of fast-track most likely extend to gynecology, although so far have scarcely been reported. There is an existing research showed FTS in gynecological oncology provide early hospital discharge after gynaecological surgery meanwhile with high levels of patient satisfaction

The aim of this study is to identify patients following a FTS program who have been discharged earlier than anticipated after major gynaecological/gynaecological oncologic surgery and analyze the complication after surgery.

Methods/Design

Comparison of Fast-Track (FT) and traditional management protocols.

the **primary endpoints** is length of hospitalization post-operation (d, mean \pm SD). It was calculated by the difference between date of discharge and date of surgery. The **secondary endpoints** are complications in both groups are assessed during the first 21 days postoperatively. Including infection(wound infection, lung infection, intraperitoneal infection, operation space infection), postoperative nausea and vomiting (PONV) , ileus, postoperative hemorrhage, postoperative thrombosis and APACHE II score.

Discussion

The advantages of fast-track most likely extend to gynecology, although so far have scarcely been reported. NO randomised controlled trials for now. The aim of this study is to compare the LOS(Length of hospitalization post-operation) after the major gynaecological/gynaecological oncologic surgery and analyze the complication after surgery. This trial can show whether the FTS program can achieve early hospital discharge after gynaecological surgery meanwhile with low levels of complications.

Background

Fast-track surgery (FTS) pathway, also known as enhanced recovery after surgery (ERAS), was initiated in 1995 by Bardram et al [1]. FTS is a multidisciplinary approach aiming to accelerate recovery, reduce complications, minimize hospital stay without an increased readmission rate and reduce healthcare costs, all without compromising patient safety [2]. The FTS pathway have been adopted by most surgical specialties worldwide, and it has been used successfully in non-malignant gynecological surgery [3, 4], but it has been proven to be especially effective in elective colorectal surgery [5-7].

The speed of postoperative recovery is influenced by multiple factors such as occurrence of pain, postoperative nausea and vomiting (PONV), paralytic ileus, fatigue and sleep disturbances. A multimodal approach to prevent and minimize these factors is considered to be essential in order to enhance recovery [2, 5, 6, 8]. Fast-track principles include a series of elements such as providing the patient with thorough preoperative information and education concerning pre-, per- and postoperative care, the use of safe and short-acting anesthetics and optimal dynamic pain relief with minimal use of opioids, management of PONV, enteral nutrition and early mobilization, and use of minimal invasive surgery [9].

The advantages of fast-track principles that have been documented in connection with abdominal surgery most likely extend to the field of gynecology, but this is only an assumption, since fast-track in elective gynecological surgery has not been studied carefully so far. There is an existing research showed FTS in gynecological oncology provide early hospital discharge after gynaecological surgery meanwhile with high levels of patient satisfaction [10]. However, no consensus guideline has been developed for gynecological oncology surgery although surgeons have attempted to introduce slightly modified FTS programmes for patients undergoing such

surgery .NO randomised controlled trials for now[3, 11, 12].

In contemporary surgical care patients would often be admitted to hospital the day prior to planned surgery, undergo preoperative mechanical and antibiotic bowel preparation and have IV fluids running to keep them in fluid balance, prior to any surgical or anaesthetic insult. Intraoperatively patients were often volume loaded to maintain a filling pressure, as well as pelvic drains to prevent development of collections, then spent 2 - 3 days nil by mouth (NBM) until bowel sounds were heard before being commenced on a graduated diet of clear liquids, free fluids, light diet and finally commenced on a regular diet 5 - 7 days post surgery. Patients were then discharged, on average 5 - 7 days post surgery[13]. Fast Track Surgery (FTS) or Enhanced Surgical Recovery (ESR) programs have been developed and refined in many specialties with documented improved patient outcomes and as a consequence earlier discharge from hospital and reduced length of stay (LOS)[2, 14, 15].

The aim of this study is to identify patients following a FTS program who have been discharged earlier than anticipated after major gynaecological/gynaecological oncologic surgery and analyze the complication after surgery.

Methods/Design

Objectives and hypothesis

Comparison of Fast-Track (FT) and traditional management protocols.

The following hypotheses will be tested:

H0: The recovery and postoperative complications is equal in both groups.

H1: The recovery was enhanced and postoperative complications is different in both groups.

Study population and eligibility criteria

The trial is designed as a randomized, controlled, nonblinded and single-center trial.

The centre: Department of gynecological oncology of Si Chuan Cancer Hospital Chengdu, Sichuan, China

Detailed inclusion and exclusion criteria are described below.

Inclusion criteria

1. Patients scheduled for gynecological oncology surgery (including radical hysterectomy add lymphadenectomy, hysterectomy add lymphadenectomy and cytoreductive).
2. Aged 18 years or older
3. Signed informed consent provided

Exclusion criteria

1. Patients with a documented infection at the time of operation.
2. Aged 71 years or older.
3. Patients with ileus at the time of operation.
4. Patients with hypocoagulability.
5. Patients with psychosis, Alcohol dependence or drug abuse history;

6. Patients with primary nephrotic or hepatic disease;
7. Patients with severe hypertension systolic pressure ≥ 160 mmHg, diastolic pressure > 90 mmHg.

Sample size calculation

The sample size calculation is based on the Length of hospitalization post-operation. The standard deviation of length of hospitalization post-operation in the traditional group is 1.5 based on previous studies [16, 17].

We estimated the number of patients needed in a superiority trial with an effect size of 90 % and a margin of 10 (alpha 5 %, power 90 %). where $u_{\alpha} = 1.96$ and $u_{\beta} = 1.28$ and using the equation $n = [2(u_{\alpha} + u_{\beta}) \sigma / \delta]^2$, a sample size of 47 patients per group is necessary to detect a difference between the groups. With an expected dropout rate of 20%, we plan to enrol 120 patients into the study.

Postoperative data collection

A daily visit of the study patients will be made by clinical investigators or a delegated physician. All protocol-required information collected during the trial will be entered into the patient's record form. Data collected relate to 1) patient characteristics, 2) hospitalisation 3) post-operation and 4) complications. The patient characteristics collected were: age, weight, height, body mass index (BMI), medical insurance status and performance status. Hospitalization details included LOS (Length of hospitalization post-operation), the procedure performed, diagnosis, operating time, name of surgery, intraoperative estimated blood loss. Post-operation details included time to full tolerance of free fluids (days), time to full tolerance of solid food (days), time to drain removal (days). Complications details included infection (wound infection, lung infection, intraperitoneal infection, operation space infection), postoperative nausea and vomiting (PONV), ileus, postoperative hemorrhage, postoperative thrombosis and APACHE II score. (Table 1).

Primary and secondary endpoints

Primary endpoints

Length of hospitalization post-operation (d, mean \pm SD). It was calculated by the difference between date of discharge and date of surgery.

Secondary endpoints

Complications: complications in both groups are assessed during the first 21 days postoperatively. Including infection (wound infection, lung infection, intraperitoneal infection, operation space infection), postoperative nausea and vomiting (PONV), ileus, postoperative hemorrhage, postoperative thrombosis and APACHE II score. (Table 1).

Ethics, study registration and consent

This trial was approved by independent ethics committees at Sichuan Cancer Hospital and Research Institute

Board Affiliation: SichuanCHRI

[contact] Email: [contact]

The study procedures, risks, benefits and data management will be clarified with the patients before they are asked to give their informed consent to participate.

Study treatment

The surgical technique is standardized in The treatment team and the patients' families were not blinded to the study. In addition, the data collectors were not involved in the clinical management of patients to ensure statistical validity and reliability. All surgeries were performed by the same team of surgeons, and the patients were treated and nursed by the same treatment team during the peri-operative period. Post-operative complications were based on patient complaints and clinical symptoms.

Given there was no Fast-track surgery guideline in the field of gynecological oncology surgery , we refer to the guideline of gastrectomy, colorectal surgery and pancreaticoduodenectomy[18-20].(Table1)

Safety aspects

Gynecological oncology surgery is highly technically demanding procedure. In order to avoid bias based on the learning curve of the surgeons, every surgical procedure will be performed or supervised by a senior surgeon. And informed consent will be obtained from all participants,

Data collected relate to 1) patient characteristics, 2) hospitalisation 3) post-operation and 4)complications. The patient characteristics collected were: age, weight, height, body mass index (BMI), medical insurance status and per-formance status. Hospitalization details included LOS(Length of hospitalization post-operation), the procedure performed, diagnosis, operating time, name of surgery, intraoperative estimated blood loss. Post-operation details included time to full tolerance of free fluids (days), time to full tolerance of solid food (days), time to drain removal (days). Complications details included infection(wound infection, lung infection, intraperitoneal infection, operation space infection), ileus, postoperative hemorrhage, postoperative thrombosis and APACHE II score. (Table 2).

Methods for avoiding bias

Minimizing systemic bias

Patients will be randomized to one of the two groups after admitting diagnosis. Randomization will be accomplished using balanced permutation blocks by generation of random numbers in order to obtain homogeneity between groups. Opaque, sealed envelopes will be produced, labelled with the randomization number

and containing a sheet that states the group allocation for the patient. Randomization envelopes will be used in consecutive order. Basic characteristics of the patient and the day of randomization will be documented on a data sheet so that compliance to the randomization scheme may be checked retrospectively. If patients are excluded from the study after randomization, their numbers will not be reused. Obviously, operating surgeons, attending physicians and nursing staff and the patients and families cannot be blinded, as the procedure is different. However, outcome assessors will be blinded. The randomization process will follow the CONSORT guidelines (Figure 1)[21].

Minimizing treatment bias

gynecological oncology surgery (including radical hysterectomy add lymphadenectomy, hysterectomy add lymphadenectomy and cytoreductive) are standardized in both group, all surgeons participating in the study are familiar with them. common procedure performed on a routine basis, which eliminates a learning curve.

Minimizing measurement bias

Detection an length of hospitalization post-operation and postoperative complications, which are the primary and secondary endpoints, will be based on data in the patient's record form. Blinding is not necessary, because the length of hospitalization post-operation is an objective endpoint that cannot be influenced by the patient. Physician blinding is not possible, because they are involved during surgery.

Statistical methods

Each patient's allocation to the analysed population will be defined prior to the analysis and will be documented. In the full-analysis set, patients will be analysed as randomized according to the intention-to-treat principle. The intention-to-treat principle implies that the analysis includes all randomized patients. The per-protocol analysis set will include all the patients without major protocol deviation. Deviations from the protocol will be assessed as major or minor. Patients with major deviations from the protocol will be excluded from the per-protocol analysis. The safety analysis set will analyse patients according to the treatment.

The null hypothesis assumes that the length of hospitalization post-operation and postoperative complications is equal in both groups. A binary logistic regression will be applied in order to compare length of hospitalization post-operation in the groups adjusting for other factors.

Data were analyzed by SPSS19.0 (SPSS Inc Chicago, Illinois) and expressed as mean \pm SD. Length of hospitalization post-operation in the FTS and traditional groups were compared and analyzed by Mann-Whitney U-tests (non-normal distribution).

NRS2002 scores between the two groups were analyzed with the Wilcoxon test (nonnormal distribution) or with Student's t-tests (normal distribution). The chi-square test or Fisher's exact test will be used for analysis of categorical secondary endpoints (complications). A P-value <0.05 will be considered statistically significant. Statistical analyses will be performed using SPSS19.0 (SPSS Inc Chicago,

Illinois).

Discussion

Fast-track surgery (FTS) pathway have been adopted by most surgical specialties worldwide, but in gynecological malignant surgery is sparingly described[22] and there are currently no randomized controlled trials to support or refute employing this approach[11]. This needs to be explored right now.

However, no consensus guideline has been developed for gynecological oncology surgery although surgeons have attempted to introduce slightly modified FTS programmes for patients undergoing such surgery .NO randomised controlled trials for now[3, 11, 12].

Widespread education is needed to improve the rate of implementation of fast-track. There are several possible reasons for this, including lack of collaboration in the surgical team and lack of awareness of or failure to accept and adopt evidence-based findings[8, 9, 23]. Close cooperation between the surgical, anesthesiological and nursing staff is essential and the importance of cooperation cannot be overestimated as practice needed to achieve further development of surgical care and postoperative recovery[24, 25]. Fast-track regimens in general have been well evaluated regarding medical complications and they appear to be safe[26].

The aim of this study is to compare the LOS(Length of hospitalization post-operation) after the major gynaecological/gynaecological oncologic surgery and analyze the complication after surgery. This trial can show whether the FTS program can achieve early hospital discharge after gynaecological surgery meanwhile with low levels of complications.

Trial status

At the time of writing, we are about to enroll patients and the anticipated study completion date is April 2017.

Abbreviations

Abbreviations	Definition
FTS	Fast-track surgery
LOS	Length of hospitalization post-operation
PONY	postoperative nauseaand vomiting

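### Scheduled operation is named neither as a stratification factor nor in the Mann-Whitney test of postoperative stay: validity is intact, but precision may be forgone, by an amount the documents cannot fix

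*Combined protocol and SAP*

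**What the plan says.** Inclusion criterion 1 admits "Patients scheduled for gynecological oncology surgery (including radical hysterectomy add lymphadenectomy, hysterectomy add lymphadenectomy and cytoreductive"; patients therefore enter with an operation already planned. Under Minimizing systemic bias, patients are randomised once the admitting diagnosis is made, and "Randomization will be accomplished using balanced permutation blocks by generation of random numbers in order to obtain homogeneity between groups". The same section adds that "Randomization envelopes will be used in consecutive order". It gives no block size and no stratification factor.

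Statistical methods compares LOS between the two arms by a Mann-Whitney test with no strata or covariates. The same section also states: "A binary logistic regression will be applied in order to compare length of hospitalization post-operation in the groups adjusting for other factors". It names neither the other factors nor the cut-point that would turn a stay in days into a yes/no outcome.

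The hospitalisation items collected are LOS and "the procedure performed, diagnosis, operating time, name of surgery, intraoperative estimated blood loss". None is identified as the operation scheduled at randomisation. The sample size section states: "The standard deviation of length of hospitalization post-operation in the traditional group is 1.5 based on previous studies [16, 17"]. It does not say whether that SD describes one operation or the mix.

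**The concern.** Cytoreductive surgery and the two kinds of hysterectomy with lymphadenectomy may plausibly lead to different stays, whatever the perioperative pathway. If they do, the difference between operations is noise in a two-group rank test. Scheduled operation is fixed before allocation, so it can be used to remove that noise without risk of bias.

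The logistic regression does not fill the gap as written. With no named factors it may or may not include operation. With a dichotomised outcome it returns an odds ratio, not an adjusted difference in days, which is the scale of the primary endpoint.

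What is at stake is power and the width of the confidence interval, not the validity of the comparison.

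**Working it through.** **Reproducing the plan's figure.** Inputs from Sample size calculation: 1.96, 1.28 and SD 1.5 (taken as days). No difference in days is given. The printed equation with a difference of 1 day gives [2 × (1.96 + 1.28) × 1.5 / 1]² = 9.72² = 94.5. That is the total; half is 47.2, matching the stated 47 per group. Back-solving the standard formula gives 1.5 × 3.24 × √(2/47) = 1.003 days, so 1 day is assumed below. (Reading the printed equation as a per-group number implies 2 × 3.24 × 1.5 / √47 = 1.42 days. A larger effect pushes both tests towards 100% power and narrows any gap.)

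After 20% dropout, 120 × 0.8 / 2 = 48 per arm. If all randomised patients are analysed, as the intention-to-treat statement requires, there are 60 per arm.

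**What drives the loss.** Put the three operation means at -g, 0 and +g days, with shares p1, p2 and p3. The between-operation variance is g² × [(p1 + p3) - (p3 - p1)²]. At g = 1:
- equal thirds: 0.667
- 80/15/5: 0.85 - 0.75² = 0.2875
- 60/30/10: 0.70 - 0.50² = 0.45
- 45/10/45: 0.90 - 0 = 0.90

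If 1.5 is the SD within one operation, the mixed-arm SD with equal thirds at g = 1 is √(2.25 + 0.667) = 1.71. If 1.5 is the SD of the mixed arm, the within-operation SD is √(2.25 - 0.667) = 1.26.

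**Normal approximation.** With 47 per group, power = Φ(1 / (SD × √(2/47)) - 1.96). SD 1.5 gives 0.898 and SD 1.71 gives 0.810.

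**Simulation of the actual tests.** Assumptions: blocks of 4 in a single series (block size and single series assumed), whole-day LOS, tie-corrected tests, two-sided 5%, 48 per arm, 1-day effect, same SD in both arms. Cells show Mann-Whitney power, then van Elteren power, then the gap in points.

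| Mix | g (days) | Between variance | 1.5 = mixed-arm SD | 1.5 = within-operation SD |
|---|---|---|---|---|
| any | 0 | 0 | 87.5%, 86.4%, about -1 | same |
| equal thirds | 0.25 | 0.04 | gap about -1 | gap about -1 |
| equal thirds | 0.5 | 0.17 | 87%, 89%, +1.4 | 85%, 86%, +1.1 |
| 80/15/5 | 1 | 0.29 | 88%, 90%, +2.7 | 84%, 86%, +2.9 |
| 60/30/10 | 1 | 0.45 | 88%, 92%, about +4 | 81%, 86%, about +5 |
| equal thirds | 1 | 0.67 | 87%, 95%, +8.3 | 78%, 86%, +8.5 |
| 45/10/45 | 1 | 0.90 | gap +11.2 | gap +12.3 |
| equal thirds | 1.5 | 1.50 | 85%, almost 100%, about +15 | 67%, 87%, about +20 to +21 |

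The gap follows the between-operation variance, not the inequality of the shares as such: 80/15/5 narrows it and 45/10/45 widens it. At 60 per arm with equal thirds and g = 1 the gaps are +5.0 (mixed-arm SD) and +6.7 (within-operation SD); at g = 0 the gap is -0.6. Right-skewed LOS (skewness 1) at 48 per arm gives -0.8 at g = 0 and +9.5 at g = 1 with within-operation SD 1.5.

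**Validity.** With unstratified blocks, g = 1 and within-operation SD 1.5, type I error was 4.8% to 5.1% for both tests. This includes 80/15/5 with no merging of sparse strata.

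**Interval width.** Mean 95% CI half-width with equal thirds and 48 per arm, unadjusted then adjusted for operation: at g = 1, 0.62 then 0.54 day (mixed-arm SD) or 0.70 then 0.64 day (within-operation SD); at g = 0, 0.62 then 0.64 day, a small loss.

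**The case against.** Unstratified blocks with an unadjusted rank test are a legitimate design. The documents give no LOS by operation and no case mix; the only average, 5 to 7 days, is for surgical care in general. The 1-day effect is back-solved, and g, the mix and the block size are assumed, so no loss is demonstrated. If operations differ only slightly, stratifying costs a little power. The logistic regression might include operation type, and its missing details are a separate specification gap. Changing the main test in a nonblinded trial carries its own risk, and a rank test reported beside a mean difference can disagree with it.

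Most of this stands, and it limits the point to an optional improvement. It does not remove it: scheduled operation is available, the regression as written gives no adjusted difference in days, and the cost in power is about 1 point.

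A reader might infer that the lack of stratification biases the LOS comparison. It does not; error rates hold. A reader might infer that the trial is underpowered. The sample size statement most naturally describes the SD of the mixed traditional arm. On that reading operation type takes essentially nothing from planned power in most of the scenarios (about 87% or more, against 87.5% at g = 0). One of the two cited sources, by its title, concerns a single operation, so the within-operation reading cannot be excluded, but nothing confirms it. Nor do the documents say that there is only one envelope series or that the Mann-Whitney test outranks the regression; they simply name no stratification factor and no ranking.

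**Conclusion.** The point holds as one of precision. Scheduled operation is used neither in the described allocation nor in the Mann-Whitney test of LOS, and the one adjusted analysis is too loosely specified to supply the missing comparison in days.

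Under the stated assumptions, the effect on power of using it runs from a loss of about 1 point (g up to about 0.25) to gains of about 8 points at g = 1 with equal thirds, about 12 with 45/10/45, and more beyond. The value g = 1 is an illustration, not an upper limit, and stratification is not guaranteed to help whenever operations differ.

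The meaning of SD 1.5 decides only how to describe the result. If it is the mixed-arm SD, planned power is kept and a possible gain is forgone. If it is a within-operation SD, the planned test falls below plan, to 78% at g = 1 with equal thirds and 48 per arm. The documents do not settle which applies.

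**What to change.** Before LOS is seen by arm, and in a dated change:

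1. Pre-specify a van Elteren (stratified Wilcoxon) test by scheduled operation for the primary LOS comparison.
2. Replace the binary logistic regression of LOS with a linear model of LOS on arm and scheduled operation, reporting the difference in days with a robust (HC3) 95% CI. State that the van Elteren test decides significance and the model gives the estimate, in case the two disagree.
3. Record the scheduled operation on the form already planned, where "Basic characteristics of the patient and the day of randomization will be documented on a data sheet". State in advance how operations outside the three named types are coded.

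If LOS by arm has already been seen, keep the Mann-Whitney test and report the stratified analysis as a sensitivity analysis. The date matters: the trial is nonblinded, people who designed it also perform the analysis, and the document is dated January 2017 with completion expected in April 2017.

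Stratified envelopes are optional, and only together with the stratified test. With stratified envelopes, equal thirds, g = 1 and within-operation SD 1.5, the Mann-Whitney type I error fell to 2.8%, while van Elteren stayed at 5.2% to 5.3%.

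Cost: about 1 point of power if operation type matters little or not at all, one data item, SAP wording, and possibly software beyond SPSS 19.0. No extra patients are needed and no treatment changes.

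### The only adjusted analysis of length of stay is a binary logistic regression with no cut-off and no named covariates, and it is not ranked against the Mann-Whitney test of the same endpoint

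*Combined protocol and SAP*

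**What the plan says.** Under Primary endpoints, length of stay is a count of days, summarised as mean and SD: "It was calculated by the difference between date of discharge and date of surgery". The Sample size calculation treats it the same way, using a formula for means: "The standard deviation of length of hospitalization post-operation in the traditional group is 1.5 based on previous studies".

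Statistical methods then gives two analyses of this endpoint. The adjusted one is: "A binary logistic regression will be applied in order to compare length of hospitalization post-operation in the groups adjusting for other factors". The unadjusted one is: "Length of hospitalization post-operation in the FTS and traditional groups were compared and analyzed by Mann-Whitney U-tests (non-normal distribution". One significance threshold, P<0.05, is set for everything. Neither analysis is called primary, secondary or supportive, and neither is assigned to the full-analysis or per-protocol set.

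No covariate list appears. Under Minimizing systemic bias, randomisation uses permuted blocks with no stratification factors, so the design does not supply one. Postoperative data collection lists baseline items ("The patient characteristics collected were: age, weight, height, body mass index (BMI), medical insurance status and performance status") alongside hospitalisation details ("the procedure performed, diagnosis, operating time, name of surgery, intraoperative estimated blood loss").

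**The concern.** Binary logistic regression needs a two-valued outcome. To use it on stay, the days must be split at a cut-off, and the plan neither gives one nor says when it would be fixed. The result would be an odds ratio for a long stay, not a difference in days, which is how the endpoint is defined and the trial sized. A pre-specified split is usable but discards information, and here the answer depends on a number left open.

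The adjustment set is equally open. Randomisation comes early ("Patients will be randomized to one of the two groups after admitting diagnosis"), so operating time and blood loss arise after allocation. Adjusting for such items can distort the treatment comparison, and nothing excludes them.

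With two unranked analyses of the primary endpoint, one may be significant and the other not, and the plan does not say which counts. If either may count, the false-positive rate exceeds 5%. Treating staff are unblinded, so choices left open could be made with results in view.

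**Working it through.** **Inputs from the Sample size calculation.** SD 1.5; multipliers 1.96 and 1.28; 47 per group; 20% dropout; 120 enrolled. No difference in days is stated; the text gives only "an effect size of 90 % and a margin of 10".

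**Difference implied by 47 per group.**
- Usual two-mean formula: √2 × (1.96 + 1.28) × 1.5 / √47 = 1.00 day.
- Printed equation read as per-group n: 2 × (1.96 + 1.28) × 1.5 / √47 = 1.42 days.

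At 1 day the printed equation gives [2 × 3.24 × 1.5 / 1]² = 94.48, which is 47.24 per group if read as a total. Dropout: 47 / 0.8 = 58.75, so 59 per group and 118 in all, close to 120. Both differences are carried forward.

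**Assumptions not in the documents.** Traditional mean 6 days; SD 1.5 in both arms; whole days; normal or lognormal stay.

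**Closed-form check (normal, 1 day, 47 per group).**
- Stay in days: 1 / (1.5 × √(2/47)) = 3.23; 3.23 − 1.96 = 1.27; power 89.8%.
- Stay split at >5 days (boundary 5.5 after rounding): proportions 0.6306 and 0.3694, pooled 0.5. (0.2612 − 1.96 × √(2 × 0.25/47)) / √(2 × 0.6306 × 0.3694/47) = (0.2612 − 0.2022) / 0.0996 = 0.592; power 72.3%. Reaching 90% at this cut-off would take 75 per group.

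**Simulated power, 47 per group** (10,000 trials per scenario; logistic is an unadjusted likelihood-ratio test of arm):

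| Difference, distribution | Mann-Whitney | >4 d | >5 d | >6 d | >7 d |
|---|---|---|---|---|---|
| 1.00 day, normal | 86.8% | 67.1% | 71.9% | 66.6% | 46.6% |
| 1.00 day, lognormal | 90.5% | 84.8% | 75.9% | 54.4% | 30.0% |
| 1.42 days, normal | 99.2% | 93.7% | 94.9% | 90.1% | 69.6% |
| 1.42 days, lognormal | 99.6% | 98.9% | 95.3% | 78.7% | 47.0% |

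**All 120 patients (60 per group).** At 1 day, Mann-Whitney has 93.9% (normal) or 96.1% (lognormal), against 57.5–83.8% or 38.0–92.2% for logistic. At 1.42 days, 99.9% against 79.9–98.5% or 56.6–99.7%.

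**One test significant and the other not, 47 per group.** At 1 day, 17.0–44.8% of trials (normal) or 11.7–61.5% (lognormal), depending on cut-off. At 1.42 days, 4.5–29.9% or 1.1–52.6%.

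**No true difference, 47 per group.** Mann-Whitney alone 4.7–5.3%; Mann-Whitney or one fixed cut-off 7.0–9.2%; Mann-Whitney or any of the four cut-offs 16.6–17.1% (14.2–14.4% with Wald tests).

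**The case against.** The strongest defence is that the Mann-Whitney test is naturally the main comparison. It is named for the primary endpoint with a distributional reason, while the logistic sentence describes itself as an adjustment. On that view what remains is an under-specified supportive model and one missing sentence. But the distributional remark explains the choice of test and does not rank it, and the logistic sentence comes first, directly after the null hypothesis.

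A second defence is that arm could be the binary outcome, with stay in days as a predictor, which needs no cut-off. Simulated unadjusted at 47 per group and 1 day, that model has 88.6% power under either distribution, against 86.5% (normal) and 90.8% (lognormal) for Mann-Whitney in the same run. The two disagree in 4–5% of trials, and counting either as success under the null gives 5.8–6.3%. The numerical consequences would largely vanish. However, the text says the model compares stay between the groups; it does not describe this reversal. Covariates and ranking would remain open, and no adjusted difference in days would result.

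Several qualifications do stand:
- Disagreement here means one P-value below 0.05 and the other above, not effects in opposite directions. Most of it is the split analysis missing the effect: at 1 day, logistic alone was significant in only 0.4–3.1% of trials at any single cut-off.
- The error inflation arises only if either test may count. The 17% is a worst case; no passage says several cut-offs will be tried.
- The simulated logistic model is unadjusted, so its power only approximates that of an adjusted one.
- Adjusting for operating time or blood loss is a risk the plan leaves open, not something it states.

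**Conclusion.** The concern holds and should be settled before analysis. The adjusted model does not fit the endpoint as defined, it cannot be run as written without an unstated cut-off, and the primary endpoint has no designated deciding analysis. None of this depends on a simulation.

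The size does depend on assumptions. With a traditional mean of 6 days, equal SDs of 1.5 and a 1-day difference, splitting stay lowers power by about 6 to 60 percentage points against Mann-Whitney at 47 per group, depending on cut-off and distribution. At 1.42 days the loss runs from under 1 to about 53 points. The Mann-Whitney test itself is workable; the fault lies in the adjusted model and the missing ranking.

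**What to change.** 1. Delete logistic regression for length of stay. It may be kept for binary complications.
2. State that the Mann-Whitney test on the full-analysis set is the single deciding analysis, reported with the Hodges-Lehmann shift in days and its 95% CI.
3. Replace the adjusted analysis with a linear regression of stay in days on arm and named baseline covariates, including the planned type of operation recorded before randomisation. Use heteroscedasticity-robust standard errors, report the adjusted mean difference with its 95% CI, and label it supportive. This estimates a different quantity from the Hodges-Lehmann shift, and the text should say so.
4. Exclude from the covariates anything that arises after randomisation, such as operating time and blood loss.

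A check of step 3 (4,000 trials, 47 per group, three-level procedure, HC3 errors) gave type I error of 4.4–5.0%. Power at 1 day was 85.2–95.7% if procedure explains 0–30% of the variance (an assumption), against 86.0–90.2% for Mann-Whitney on the same data. Making the linear model the deciding analysis is an option, provided only one analysis decides. A pre-specified, justified cut-off could also be defended, at the power cost shown.

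The cost is a wording change, slightly more analysis and one data field. The plan lists the procedure performed, so the planned procedure must be noted beforehand; this can be a line on the data sheet already completed at randomisation. No extra patients or visits are needed. Trial status says enrolment had not begun at the time of writing, so on that account the change could precede any data.
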